4.1.2 PHASE II - PHARMACOKINETIC SUB-STUDY

Patients accepting to be included in the sub-study of phase II will be enrolled sequentially until the required sample size (10 evaluable patients in each dose group) is reached. If patients do not undergo all PK evaluations, the sub-study sample size will be increased to guarantee at least 8 PK evaluations for each assessment time.

Dietary restrictions based on the INRAN tables (*Carnovale and Marletta 2007*) are required, after overnight fasting, between 24 hours before and the start of mannitol self-administration. Thus, foods containing a significant amount of soluble sugars are to be forbidden for the PK sub-study. Patients enrolled in the pharmacokinetic sub-study have to avoid any food intake and drink only water between the start of mannitol self-administration and 8 hours after mannitol intake. Of note, between 4 and 8 hours after mannitol intake, patients may eat any food devoid of soluble sugars according to the INRAN tables, if deemed necessary by the Investigator. Patients will be allowed to eat without restrictions 8 hours after drug self-administration.

Study visits

Patients enrolled in the pharmacokinetic sub-study will follow the same scheme of phase II of the study that consists of four visits:

Visit 1 (\leq 28 days before the day of colonoscopy): after signed written informed consent is obtained, information concerning demographics, medical history, concomitant medications and indications for colonoscopy will be collected in the electronic case report form (eCRF). The incidence of adverse events will be recorded.

Visit 2 (\leq 7 days before the day of colonoscopy): to complete the verification of inclusion/exclusion criteria, a blood sample will be drawn to assess the haematological and chemical parameters (including electrolyte levels) of all patients and to perform a pregnancy test for women of childbearing potential. Assessments include a urinalysis and the measurement of vital signs (blood pressure and heart rate). The incidence of adverse events will be recorded.

Visit 3 (\leq 7 days before the day of colonoscopy): if inclusion/exclusion criteria are met, the Bristol Stool Form Scale (BSFS) will be administered, randomization will be performed, study drug will be dispensed and verbal and written instructions for its use will be provided. The date and time of colonoscopy will be communicated and reported on a form given to the patient. On the same form, patients will indicate date and time of start and end of study drug self-administration. The incidence of adverse events will be recorded.

More than one visit may take place on the same day.

Visit 4 (day of colonoscopy):

A blood and urine sample will be collected at the following time points:

- 4 hours \pm 30 minutes after the end of study drug self-administration
- 8 hours \pm 30 minutes after the end of study drug self-administration

In addition, in order to measure mannitol blood levels, venous blood samples will be drawn at the following times:

- T_0 (baseline, before mannitol self-administration)
- T_1 (1 hour \pm 5 min after completion of mannitol self-administration)
- T_2 (2 hours \pm 5 min after completion of mannitol self-administration)
- T_4 (4 hours \pm 10 min after completion of mannitol self-administration, before colonoscopy)
- T_8 (8 hours \pm 10 min after completion of mannitol self-administration, after colonoscopy)

After completion of bowel preparation, prior to colonoscopy, patients will fill in the questionnaire on acceptability and adherence.

The blinded endoscopist will then perform the scheduled colonoscopy using a standard colonoscope recording data on bowel cleansing using the BBPS and measuring intestinal gas concentrations in each colon segment after standard washing and air insufflation. Of note, CO₂ insufflation and water-aided techniques for colon distension (e.g. water immersion and water exchange) will not be allowed. The endoscopist will also confirm caecal intubation, defined as identification of the appendiceal orifice. Drugs administered for the procedure will be recorded.

Intestinal gas concentrations in each segment will be measured using a multi-gas detector (Dräger X-am® 8000). Please refer to the *Gas Detector Technical Documentation* for further details. Use of any electrocautery device is allowed only during withdrawal and after washing and air insufflation. If H₂ and/or CH₄ levels are potentially dangerous, any electrosurgical procedure must be avoided.

Vital signs (heart rate and blood pressure) will be measured prior to colonoscopy. Oxygen saturation and heart rate will be measured continuously during colonoscopy, but only clinically significant abnormal findings will be recorded on the eCRF, where clinically significant means that these abnormal findings cause an additional control or a medical intervention.

The incidence of adverse events will be recorded.

4.1.3 PHASE III

A parallel-group design will be implemented to test the non-inferiority of bowel cleansing with the mannitol dose selected in phase II against standard split 2-liter polyethylene glycol plus ascorbate solution (Moviprep®). Phase III will begin only once all data collected from phase II necessary for establishing the optimal mannitol dose have been analysed. The non-inferiority study will be conducted in 4 countries (Italy, Germany, Russia and France) and involve 696 subjects randomized in a 1:1 ratio to one of the two study drugs. Randomization will be stratified by centre.

Study visits

Phase III of the study consists of four visits:

Visit 1 (≤ 28 days before the day of colonoscopy): after signed written informed consent is obtained, information concerning demographics, medical history, concomitant medications and indications for colonoscopy will be collected in the electronic case report form (eCRF). The incidence of adverse events will be recorded.

Visit 2 (≤ 7 days before the day of colonoscopy): to complete the verification of inclusion/exclusion criteria, a blood sample will be drawn to assess the haematological and chemical parameters (including electrolyte levels) of all patients and to perform a pregnancy test for women of childbearing potential. Assessments include a urinalysis and the measurement of vital signs (blood pressure and heart rate). The incidence of adverse events will be recorded.

Visit 3 (\leq 7 days before the day of colonoscopy): if inclusion/exclusion criteria are met, randomization will be performed, study drug will be dispensed and verbal and written instructions for its use will be provided. The date and time of colonoscopy will be communicated and reported on a form given to the patient. On the same form, patients will indicate date and time of start and end of study drug self-administration. The incidence of adverse events will be recorded.

More than one visit may take place on the same day.

Visit 4 (day of colonoscopy):

A blood and urine sample will be collected at the following time points:

- 4 hours \pm 30 minutes after the end of study drug self-administration
- 8 hours \pm 30 minutes after the end of study drug self-administration

After completion of bowel preparation, prior to colonoscopy, patients will fill in the questionnaire on acceptability and adherence. The Bowel Cleansing Impact Review (BOCLIR) is also to be completed, but only by patients enrolled at Italian centres.

The blinded endoscopist will then perform the scheduled colonoscopy using a standard colonoscope recording data on bowel cleansing using the BBPS and Ottawa scale. The endoscopist will confirm caecal intubation, defined as identification of the appendiceal orifice, and record the number, appearance, size, location and histological type of neoplastic and inflammatory colorectal lesions detected.

The endoscopist will measure intestinal gas concentrations in each colon segment after standard washing and air insufflation. Of note, CO₂ insufflation and water-aided techniques for colon distension (e.g. water immersion and water exchange) will not be allowed. H₂, CH₄ and O₂ levels are also to be measured following the introduction of the colonoscope in the sigmoidal-rectum junction (15-25 cm from anal margin) before standard washing and air insufflation. Drugs administered for the procedure will be recorded.

Intestinal gas concentrations in each segment will be measured using a multi-gas detector (Dräger X-am® 8000). Detailed information is available in the *Gas Detector Technical Documentation*. Use of any electrocautery device is allowed only during withdrawal and after washing and air insufflation. If H₂ and/or CH₄ levels are potentially dangerous, any electrosurgical procedure must be avoided.

Vital signs (heart rate and blood pressure) will be measured prior to colonoscopy. Oxygen saturation, blood pressure and heart rate will be measured during colonoscopy, but only clinically significant abnormal findings of oxygen saturation and heart rate measured during colonoscopy and blood pressure measured immediately prior and after colonoscopy will be recorded on the eCRF, where clinically significant means that these abnormal findings cause an additional control

or a medical intervention. Of note, clinically significant changes of blood pressure measured during colonoscopy will also be reported if considered clinically significant by the Investigator.

The incidence of adverse events will be recorded.

4.2 END OF STUDY DEFINITION

A participant is considered as having completed the study if he or she has completed the procedures in the SoA. Of note, the results of the laboratory tests performed at Visit 4 (day of colonoscopy) and the histological evaluation of colorectal lesions detected during colonoscopy will be available after the participant has completed the last procedure of the study on the day of colonoscopy. The end of the phase II/III study is defined as completion of the last procedure in the trial globally, namely the last visit of the last patient enrolled in the phase III study (i.e. last patient last visit, LPLV).

5 STUDY POPULATION

The study population is made up of 846 adult patients scheduled for elective (screening, surveillance or diagnostic) colonoscopy; 50 patients in each of the three mannitol dose groups for phase II, and 348 patients in each of the two treatment groups for phase III (the selected mannitol dose and 2L PEG ASC). The population for phase III will not include the patients who participated in phase II.

5.1 INCLUSION CRITERIA

To be eligible to participate in this study, a subject must meet all the following criteria:

1. Ability of patient to consent and provide signed written informed consent
2. Age ≥ 18 years
3. Males and females scheduled for elective (screening, surveillance or diagnostic) colonoscopy to be prepared and performed according to ESGE guidelines
4. Patients willing and able to complete the entire study and to comply with instructions

5.2 EXCLUSION CRITERIA

An individual who meets any of the following criteria will be excluded from participation in this study:

1. Pregnancy or breast feeding. Females of childbearing potential must have a negative pregnancy test at Visit 2 and must practice one of the following methods of birth control throughout the study period (unless postmenopausal or surgically sterile, or whose sole sexual partner has had a successful vasectomy): oral, implantable, or injectable contraceptives (for a minimum of three months before study entry) in combination with a condom; intrauterine device in combination with a condom; double barrier method (condom and occlusive cap with spermicidal foam/gel/film/cream/suppository).
2. Severe renal failure: glomerular filtration rate (eGFR) < 30 ml/min/1.73 m² estimated by means of simplified MDRD equation.
3. Severe heart failure: NYHA Class III-IV.
4. Severe anaemia (Hb ≤ 8 g/dl).
5. Severe acute and chronically active Inflammatory Bowel Disease; patients in clinical remission (Crohn's Disease Activity Index - CDAI < 150 for Crohn Disease (*Best et al., 1976*) and Partial Mayo Score ≤ 2 for Ulcerative Colitis (*Schroeder et al., 1987*) are allowed.
6. Chronic liver disease Child-Pugh class B or C.
7. Electrolyte disturbances (Na, Cl, K, Ca or P out of normal ranges)
8. Recent (< 6 months) symptomatic acute ischemic heart disease.

9. History of significant gastrointestinal surgeries, including colon resection, sub-total colectomy, abdominoperineal resection, de-functioning colostomy or ileostomy, Hartmann's procedure and other surgeries involving the structure and function of the colon.
10. Use of laxatives, colon motility altering drugs and/or other substances (e.g. simethicone) that can affect bowel cleansing or visibility during colonoscopy within 24 hours prior to colonoscopy.
11. Suspected bowel obstruction or perforation.
12. Indication for partial colonoscopy.
13. Patients who have received an investigational drug or therapy within 5 half-lives of the first visit.
14. Patients previously screened for participation in this study.
15. Hypersensitivity to the active ingredients or to any of the excipients of the study drugs.
16. Contraindications to Moviprep® (only for phase III).

5.3 SCREEN FAILURES

Screen failures are defined as participants who consent to participate in the clinical trial but do not subsequently begin the investigational treatment. A minimum set of screen failure information is required to ensure transparent reporting of screen failure participants, to meet the Consolidated Standards of Reporting Trials (CONSORT) publishing requirements and to respond to queries from regulatory authorities. Minimal information includes demography, screen failure details, eligibility criteria, and any serious adverse event (SAE).

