4 STUDY DESIGN

4.1 OVERALL DESIGN

This is a phase II/III, international, multicentre, randomized, parallel-group, endoscopist-blinded study that combines a phase II dose-finding study/pharmacokinetic sub-study with a phase III non-inferiority efficacy study (see [Figure 4-1](#)). The population for phase III will not include the patients who participated in phase II.

Figure 4-1 Study design

In both phases, the study drugs will not be blinded, but all endoscopists performing study colonoscopies will not be aware of group allocation; patients and site personnel involved in the randomization of the patient and management of the study drugs will be instructed not to disclose group allocation to the endoscopists. Experienced endoscopists will undergo specific training to decrease inter-observer variability in the evaluation of bowel cleansing and to refine intestinal gas measurement techniques.

Details of all the assessments to be performed are available in the schedule of activities (SoA) in [Section 1.2](#) and in [Section 8](#).

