- 4) Drink about one litre of clear liquid in the next hour according to local practice at the centre to prevent dehydration. Patients enrolled in the pharmacokinetic sub-study should drink only one litre of water in the next hour and follow the dietary restrictions and fasting instructions previously described.

Participants will be instructed to drink mannitol **the day of the colonoscopy** and self-administration must be completed at least 4 hours before colonoscopy.

2L PEG ASC (Moviprep®)

The route of administration is oral. One treatment consists of two litres of Moviprep® taken according to split-dose regimen. During treatment it is strongly recommended to drink about half a litre (500 mL) of clear liquid after each litre of Moviprep® to prevent dehydration, according to local practice at the centre.

The first litre of Moviprep® is prepared by dissolving one sachet A and one sachet B together in water to make one litre of solution. The reconstituted solution must be drunk over a period of one to two hours **the evening before colonoscopy**. About half a litre of clear liquid should be drunk in the next hour to prevent dehydration according to local practice at the centre. This process should be repeated with a second litre of Moviprep® prepared by dissolving one sachet A and one sachet B together in water to make one litre of solution in the early morning of the **day of the procedure**. As previously mentioned, about half a litre of clear liquid should be drunk in the next hour to prevent dehydration according to local practice at the centre. Ensure consumption of Moviprep® as well as of any other clear fluids has finished at least four hours before the start of colonoscopy.

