9.2 RANDOMIZATION

At Visit 3, all eligible subjects will be randomized via eCRF to one of the treatment groups according to the study phase. The Investigator or his/her delegate will confirm that the subject has fulfilled all the inclusion/exclusion criteria in the eCRF. The eCRF will assign a randomization number to the subject, which will be used to link the subject to the treatment and will specify a unique medication number for the package of study treatment to be dispensed to the subject. The subject's randomization number will not be shown in the eCRF: only the medication number will be made available.

For each phase of the study a stratified subject randomization list will be produced in balanced blocks through a validated SAS program.

Phase II – dose finding: the randomization will be stratified by centre and by the presence of constipation (yes/no), defined as the recurrent use of laxatives or Bristol Stool Form Scale (BSFS) < 3 in the two weeks before randomisation.

Phase III – non-inferiority: the randomization will be stratified by centre.

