9.3 POPULATIONS FOR ANALYSES

The following populations will be used for the statistical analyses:

- Safety set: all patients who take the study preparation, even only partially. Patients will be analysed according to the study drug dose actually received.
- Modified Safety set: all patients who take the study preparation, even only partially, and who do not meet significant protocol violations that regard inclusion/exclusion criteria. Patients will be analysed according to the study drug dose actually received.
- PK population (only for the pharmacokinetic sub-study): all randomized patients who complete the mannitol treatment and have at least one PK assessment, regardless of the outcome of colonoscopy. Patients will be analysed according to the study drug dose actually received.
- Full Analysis Set (FAS): all randomized patients who take the study preparation, even only partially, undergo the colonoscopy, and have a BBPS available for at least one colon segment after standard washing and air insufflation for luminal distension. According to the Intention to Treat (ITT) principle, patients will be analysed according to the study drug dose assigned at randomization.
- Per protocol (PP): all randomized patients who meet the following criteria:
 - Treatment with the study drug completed.
 - Colonoscopy completed adequately in absence of pathological obstruction that prevents reaching the right colon, including the cecum (i.e. endoscope does not find obstacles other than faecal material) and without acute deterioration of general conditions causing procedure suspension.
 - Bowel cleansing assessment and gas measurement are available for all colon segments after standard washing and air insufflation for luminal distension.
 - No significant protocol violations that regard inclusion/exclusion criteria or that can condition evaluations.

Patients will be analysed according to the study drug dose actually received.

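### Section 5.3 defines screen failure by not starting treatment rather than by not being randomised, and no planned analysis or by-arm report covers randomised patients who never start

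*Combined protocol and SAP*

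**What the plan says.** **The definition.** Section 5.3 reads: "Screen failures are defined as participants who consent to participate in the clinical trial but do not subsequently begin the investigational treatment". It makes no exception for patients already randomised. It asks for a minimum record covering demography, eligibility, failure details and SAEs, and gives CONSORT reporting as one reason. The assigned arm is not on that list.

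**Order of events.** Section 9.2 states: "At Visit 3, all eligible subjects will be randomized via eCRF to one of the treatment groups according to the study phase". Section 4.1.3 places Visit 3 no more than 7 days before colonoscopy, and at that visit "randomization will be performed, study drug will be dispensed and verbal and written instructions for its use will be provided". Intake follows. Under 6.1.2 the first litre of Moviprep is taken the evening before. Mannitol is taken on the day, and "self-administration must be completed at least 4 hours before colonoscopy". Section 4.1 says that "the study drugs will not be blinded, but all endoscopists performing study colonoscopies will not be aware of group allocation", so patients know their arm before they decide whether to start.

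**Other statuses.** Section 7.2 covers withdrawal, with the reason recorded on the eCRF. Section 7.3 covers patients who fail to appear, who are recorded as lost to follow-up.

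**Analysis sets (9.3).** The FAS is "all randomized patients who take the study preparation, even only partially, undergo the colonoscopy, and have a BBPS available for at least one colon segment". The Safety set requires at least partial intake and the PP set requires completed treatment.

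**Adherence.** Section 3 lists three levels, the last being that the drug was not taken. Section 9.4.1 analyses adherence in phase III on the FAS.

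**The concern.** Screening normally ends at randomisation. Here the label extends past it, so one patient can hold two statuses: screen failure under 5.3, and withdrawal or loss to follow-up under 7.2 or 7.3. Sites have no rule for choosing between them, and different sites may choose differently.

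The choice matters because allocation is open and the regimens differ: one dose on the day against two litres split over the evening and the morning. Refusing the assigned preparation could therefore depend on the arm. Phase III also has adherence and acceptability among its objectives, yet the one adherence level that records refusal cannot occur in the set on which adherence is analysed. If non-start differs by arm, the comparison among starters is no longer fully protected by randomisation. The plan includes no table or analysis that would let a reader see whether this happened.

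**Working it through.** **1. Trace one patient.** Take a phase III patient who consents, is eligible, is randomised and given drug at Visit 3, and takes none of it.

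| Provision | Outcome |
|---|---|
| 5.3 | Meets the screen-failure definition |
| 7.2 or 7.3 | Also a withdrawal or lost to follow-up |
| Safety set, FAS, PP (9.3) | Excluded from all three, each requiring intake |
| Adherence table (9.4.1) | Excluded, because it is run on the FAS |
| eCRF and drug accountability (9.2, 6.2.1) | Arm recoverable |
| By-arm reporting of such patients | Not required anywhere |

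**2. Reproduce the plan's sample size.** Inputs from 9.1: success 0.85 in both arms, margin 0.08, one-sided alpha 0.025, power 80%.

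n = (1.960 + 0.842)² × 2 × 0.85 × 0.15 / 0.08² = 7.849 × 0.255 / 0.0064 ≈ 312.7, so 313 per arm.

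Inflation: 626 / 0.90 = 695.6, so 696, or 348 per arm. Both figures agree with the plan, and the sample size is not in question.

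**3. What could non-start do?** The documents give no rate, so these are assumed scenarios: 348 randomised per arm, 85% success among starters in both arms, and non-starters counted as failures. With non-start proportions dS (Moviprep) and dT (mannitol):

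- pS = 0.85(1 − dS) and pT = 0.85(1 − dT)
- lower limit = pT − pS − 1.96 × √[pT(1 − pT)/348 + pS(1 − pS)/348], the Wald form in 9.4.1
- margin = −(1 − 0.906) × pS when pS is below 0.85. This carries the plan's adjustment rule over to the all-randomised analysis, which is itself an assumption.

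Worked case, dS = 3% and dT = 6%: pS = 0.8245, pT = 0.7990, difference −0.0255. The standard error is √[(0.1606 + 0.1447)/348] = 0.0296, so the lower limit is −0.0255 − 0.0581 = −0.0836. The margin is −0.094 × 0.8245 = −0.0775.

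Starters only in that case: n = 337.6 and 327.1, difference 0, and lower limit −1.96 × √[0.1275 × (1/337.6 + 1/327.1)] = −0.0543.

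| Non-start, Moviprep / mannitol | pS | pT | Difference (points) | Lower limit, all randomised | Adjusted margin | Result |
|---|---|---|---|---|---|---|
| 3% / 6% | 0.8245 | 0.7990 | −2.55 | −8.4 | −7.75 | fails |
| 2% / 3% | 0.8330 | 0.8245 | −0.85 | −6.4 | −7.83 | passes |
| 5% / 5% | 0.8075 | 0.8075 | 0 | −5.9 | −7.59 | passes |
| 6% / 3% | 0.7990 | 0.8245 | +2.55 | −3.3 | −7.51 | passes |

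The starters-only limit is about −5.4 in every row. The first row also fails against the unadjusted margin of −8.0.

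**4. Tipping point in patients.** If every Moviprep patient starts, 10 mannitol non-starters give −7.92 (passes) and 11 give −8.18 (fails against −8.0). Eleven is 11/348 = 3.2%, and the starters-only limit at that count is −5.35. With 7 Moviprep non-starters the result reverses at 16 on mannitol; with 14, at 22. The excess on mannitol is then 11, 9 or 8 patients. The plan allows for a loss of 348 − 313 = 35 per arm from all causes.

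**The case against.** The strongest reply is that 5.3 is only a label. No analysis set in 9.3 refers to screen-failure status. Non-starters leave the primary analysis because the FAS requires intake, so rewriting 5.3 alone would change no result. That is right. The contrast of −5.4 with −8.4 measures the effect of requiring intake, not of the wording in 5.3.

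A reader might infer four stronger things, and the documents support none of them.

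- *That such patients would appear in the CONSORT flow as never randomised.* No section describes the flow diagram. The FAS wording, which picks out those randomised patients who take the drug, presupposes that some do not.
- *That their arm is lost.* The 5.3 data set is a minimum. The eCRF links each subject to a treatment and a medication number (9.2), accountability is kept per subject (6.2.1), and withdrawal reasons are recorded (7.2).
- *That the FAS text contradicts itself by invoking intention to treat.* That sentence says only that patients are analysed by assigned arm. It does not claim that everyone randomised is included.
- *That the omission favours mannitol.* Section 2.2.2 expects better compliance with mannitol. If non-start is higher on Moviprep, leaving non-starters out works against mannitol, as the last row of the table shows.

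What survives is that the two statuses overlap, no planned analysis includes these patients, the lowest adherence level cannot be observed, and by-arm reporting is possible but not required.

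**Conclusion.** The point holds as one of definition and reporting, and it should be corrected. It does not show that the primary analysis is wrong or biased in a known direction.

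Under the stated assumptions, an excess of roughly 3 percentage points in non-start on mannitol would be enough for an all-randomised analysis to miss non-inferiority while the starters-only comparison passes comfortably. Smaller or equal rates, or an excess on Moviprep, would leave the conclusion standing. The rates are illustrative, and equal success among starters is the plan's own assumption of no difference applied to that group. Counting non-starters as failures is one convention, suited to a supportive analysis. The conclusion may well not change, but the plan as written does not commit to showing that.

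**What to change.** 1. In 5.3, define a screen failure as a participant who consents but is not randomised.
2. State that a randomised patient who takes no study drug is a post-randomisation discontinuation under 7.2 or 7.3, reported by arm with the reason.
3. In 9.4.1, add one supportive phase III sensitivity analysis on all randomised patients that counts non-starters as not adequately cleansed. Say which margin it is read against.
4. Tabulate adherence, including the level for drug not taken, on all randomised patients.

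Items 1 and 2 repair the participant flow, and items 3 and 4 address the analysis; neither pair substitutes for the other. The primary FAS and PP analyses stay as they are. The cost is a short text change, one eCRF status code and one extra table, with no added patients or visits. The supportive result may look less favourable than the primary one.
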